5 BIOSPECIMEN COLLECTION

5.1 CORRELATIVE–IMMUNOLOGIC STUDIES

(See Appendix D for tubes and volumes)

5.1.1 Immune cell infiltrate

Slides made from prostate biopsy specimens (collected at baseline) and prostatectomy specimens (collected at surgery performed after last dose of vaccine) will be stained for CD4 and CD8 cells and digitized for analysis of immune cell infiltrate. Other markers such as CD4/FoxP3 may also be stained for further correlative studies. These studies will be performed by the Laboratory of

Tumor Immunology and Biology. At a minimum, 5 slides from one biopsy core confirmed to contain cancer will be needed for baseline quantification. Attempts will be made based on anatomic location notation or when available, MRI based location, to correlate biopsy location with pathologic location on prostatectomy specimens. When feasible, quantitation will be performed in triplicate. Quantitation will be reported as number of stained cells per micron squared of surface area. Wilcoxon matched pair signed rank test, Friedman test with Dunn's multiple comparisons, or alternative statistical models will be used as appropriate. Aperio ScanScope digital scanner systems with Aperio ImageScope software algorithms will be used. Manual quantitation will be performed in case of software malfunction. Isotype antibodies negative controls will be included in all runs. Tonsil or lymph node tissue will be positive control for CD4 and CD8. Slides will be developed with primary and secondary antibodies per manufacturer specifications for visualization of cells.

5.1.2 Sera Antibody Analysis

Serum will be stored at -80 degrees Celsius and there will be planned analysis for generation of antibodies to PSA, BCG, PAP, PSMA, PSCA, and/or MUC-1 by the Laboratory of Tumor Immunology and Biology.

5.1.3 T-cell assays

We plan to examine the immune response in selected patients. Lymphocytes will be separated from heparinized blood using density gradient centrifugation. The lymphocytes will then be placed in human AB serum with 10% DMSO and stored in liquid nitrogen. When samples are available from pre- and post-treatment, the ELISPOT or other T-cell assay will be performed. The ELISPOT assay, measuring IFN-gamma production, is used to determine CTL precursor frequency to peptides from tumor associated antigens in both pre- and post-vaccination peripheral blood mononuclear cells, as previously described(32). These assays will be performed in the Laboratory of Tumor Immunology and Biology, NCI, NIH.

5.1.4 MRI study

If logistically feasible, an MRI will be performed at baseline before the first vaccine administration and after the last vaccine administration as part of the pre-operative workup. This will be done to assess for changes in the imaging characteristics of the prostate cancer pre and post vaccination.

Prior to entering the scanner the patient will answer the standard MRI safety checklist administered to all patients undergoing MRI in the Clinical Center to insure that it is safe to perform an MRI. Images will be reviewed for lesions suspicious for prostate cancer. Pre and post-vaccine images will be compared to assess for changes seen on MRI. These studies will be performed by the NCI Molecular Imaging Program.

5.1.5 Additional Assays

Blood and tissue samples may be used for additional research studies, which may include phenotypic and functional analysis of tumor and immune-cell subsets (such as the CD3, CD4, and CD8 subsets and CD4:CD8 ratio), Class II immune responses, CTL assay, TBNK and analyses for cytokines (IFN- γ , IL-10, IL-12, IL-2, IL-4, etc.), chemokines, antibodies, tumor associated antigens, tumor specific gene expression profiling using RT-PCR of the RNA extracted from the tumor and/or other markers. Many of these studies will aid in not only assessing response, but predictors of response.

All samples will be labeled with the following identifier system.

- Patient's enrollment #
- Trial number
- Patient's initials

Example: 01-ABC

These labels are used only to send the samples from the NIH Clinical Center to the NCI Frederick Central Repository. The NCI Repository will process all samples, appropriately discard the label on the blood tube, and then store the samples with unique identifiers, to which only NCI study personnel will have the code to link to patient specific clinical information. Samples will be tracked according to Section 5.2 (Sample Storage, Tracking and Disposition).

5.1.6 Analysis of pre and post treatment samples

5.1.6.1 Analysis of tissues using multiplexed immunofluorescence or multispectral imaging to identify specific markers, including markers of immune cell subsets, may be performed in collaboration with:

[name]
PerkinElmer
[name]
[name]
[contact]
[contact]

And

General Electric (GE) Global Research
[name].
Lifesciences and Molecular Diagnostics Org
[name]
[name]
[name]
[contact]
[contact]

5.1.6.2 RNA-based analysis may be performed in collaboration with:

- HTG Molecular Diagnostics, Inc.
[name]
[name]
[contact]
[contact]

Attention:

[name], VP Corporate Development
[contact]
[contact]

HTG Molecular Diagnostics, Inc. has a platform to obtain RNA from formalin-fixed and paraffin-embedded (FFPE) tissues and from PBMC cells. NCI would

send HTG Molecular paired coded samples of pre treatment and post treatment PBMC and FFPE slides (H&E and serial unstained slides) for analysis.

5.2 STORAGE AND TRACKING OF COLLECTED BLOOD SAMPLES

All data associated with the patient samples is protected by using a secure database. Non-clinical samples drawn at the NIH Clinical Center or collected from tissue specimens for immunological evaluation will be transported to the NCI Frederick Central Repository by the Leidos, Biomedical, Inc. couriers. The contact person for arranging transport is [name] [contact]).

Samples will be tracked and managed by Central Repository database. All samples will be stored in either a -20 or -80°C freezer. These freezers are located at NCI Frederick Central Repository in Frederick, Maryland.

American Type Culture Collection (ATCC) manages the NCI-Frederick Central Repositories under subcontract to Leidos Biomedical, Inc. NCI-Frederick Central Repositories store, among other things, biological specimens in support of NIH clinical studies. All specimens are stored in secure, limited access facilities with sufficient security, back up and emergency support capability and monitoring to ensure long-term integrity of the specimens for research.

ATCC's role is limited to clinical research databases and repositories containing patient specimens. ATCC does not conduct nor has any vested interest in research on human subjects, but does provide services and support the efforts of its customers, many of which are involved in research on human subjects.

It is the intent and purpose of ATCC to accept only de-identified samples and sample information. To the limit of our ability, every effort will be made to ensure that protected information is not sent electronically or by hard copy or on vial labels.

Sample data is stored in the BioSpecimen Inventory System II (BSI). This inventory tracking system is used to manage the storage and retrieval of specimens as well as maintain specimen data. BSI is designed for controlled, concurrent access. It provides a real-time, multi-user environment for tracking millions of specimens. The system controls how and in what order database updates and searches are performed. This control prevents deadlocks and race conditions. For security, BSI has user password access, three types of user access levels, and 36 user permissions (levels of access) that can be set to control access to the system functions. BSI provides audit tracking for processes that are done to specimens including shipping, returning to inventory, aliquoting, thawing, additives, and other processes. BSI tracks the ancestry of specimens as they are aliquoted, as well as discrepancies and discrepancy resolution for specimens received by the repository. If a specimen goes out of the inventory, the system maintains data associated with the withdraw request. Vials are labeled with a unique BSI ID which is printed in both eye readable and bar coded format. No patient specific information is encoded in this ID.

Investigators are granted view, input and withdraw authority only for their specimens. They may not view specimen data or access specimens for which they have not been authorized. Access to specimen storage is confined to repository staff. Visitors to the repositories are escorted by repository staff at all times.

Once primary research objectives for the protocol are achieved, intramural researchers can request access to remaining samples providing they have an IRB approved protocol and patient consent.

Samples, and associated data, will be stored permanently unless the patient withdraws consent. The PI will report destroyed samples to the IRB if samples become unsalvageable or destroyed by environmental conditions (ex. Broken freezer or lack of dry ice in shipping container) or if a patient chooses to withdraw his/her consent. Samples will also be reported as lost if they are lost in transit or misplaced by a researcher.

6 DATA COLLECTION AND EVALUATION

6.1 DATA COLLECTION

Data from this study will be stored in the C3D and Labmatrix databases.

1. Eligible patients must be confirmed and checklist completed. Consent form must be signed prior to registration with the NCI Central Registration Office.
2. For adverse event reporting see section 7.
3. Treatment is given according to protocol (dated notes about doses given, complications, and clinical outcomes).
4. Toxicity is assessed according to protocol (laboratory report slips, etc.)
5. Response is assessed according to protocol (X-ray, scan, lab reports, date noted on clinical assessment, as appropriate).
6. Drug Accountability Records are kept for each patient.
7. Exception will be made for the collection of Grade I toxicities.
8. Post-operatively, we will not report Grades 1 or 2 AEs that are clearly attributable to surgery. This includes, but is not limited to, anemia, nausea and pain, but will be at the PIs discretion. Post-operatively, we will not capture erectile dysfunction or incontinence as AEs.

As general anesthetics, as well as medications used for perioperative symptom management, tend to be both expected and routine, we will not capture medications administered perioperatively; however, should a patient experience a Serious Adverse Event during surgery, any medications indicated during that event would be entered into the database.

The PI will be responsible for overseeing entry of data into an in-house password protected electronic system and ensuring data accuracy, consistency and timeliness. The principal investigator, associate investigators/research nurses and/or a contracted data manager will assist with the data management efforts. All data obtained during the conduct of the protocol will be kept in secure network drives or in approved alternative sites that comply with NIH security standards. Primary and final analyzed data will have identifiers so that research data can be attributed to an individual human subject participant.

End of study procedures: Data will be stored according to HHS, FDA regulations and NIH Intramural Records Retention Schedule as applicable.

Loss or destruction of data: Should we become aware that a major breach in our plan to protect subject confidentiality and trial data has occurred, the IRB will be notified.

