Neoadjuvant use of a prostate cancer vaccine makes sense because the patient has a low volume of disease (organ confined) and has an intact immune system (surgical patients are younger, healthier, and have not been exposed to systemic therapies or have occult bone marrow metastasis as is often seen in men with metastatic castration-resistant prostate cancer who receive vaccine therapy after progressing on chemotherapy). Although no data currently exist with neoadjuvant vaccine in localized prostate cancer, outcomes with patients with lower metastatic burden have demonstrated a greater prolonged effect of delaying disease onset and progression. The patient population in this study has very low tumor burden only locally present and thus is the earliest patient population that could be treated. The potential benefits are a prolonged action of the prostate vaccine on preventing growth of any micrometastatic disease that may be present. This risk may be quite low in the low risk subgroups however is not zero in any patient. The vaccine has been demonstrated to be safe in multiple trials and thus even in the setting of uncertain benefit, this is a therapy that poses minimal risk to the patient population enrolled in the trial. A topic of interest within this study will be to examine if neoadjuvant use demonstrates similar activation of T-cell immunity as compared to use at time of metastatic disease. CD4 and CD8 cell infiltrates were chosen as primary outcome measures as they represent the immune mechanism by which the vaccine ultimately has effect and have been used in recent trials with success (32). Previous studies (29) have already demonstrated a strong correlation between T-cell infiltrate and overall vaccine efficacy for overall survival.

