7 SAFETY REPORTING REQUIREMENTS/DATA AND SAFETY MONITORING PLAN

7.1 DEFINITIONS

7.1.1 Adverse Event

An adverse event is defined as any reaction, side effect, or untoward event that occurs during the course of the clinical trial associated with the use of a drug in humans, whether or not the event is considered related to the treatment or clinically significant. For this study, AEs will include events reported by the patient, as well as clinically significant abnormal findings on physical examination or laboratory evaluation. A new illness, symptom, sign or clinically significant laboratory abnormality or worsening of a pre-existing condition or abnormality is considered an AE. All AEs must be recorded on the AE case report form unless otherwise noted above in Section 6.1.

All AEs, including clinically significant abnormal findings on laboratory evaluations, regardless of severity, will be followed until return to baseline or stabilization of event. Serious adverse events that occur more than 30 days after the last administration of investigational agent/intervention and have an attribution of at least possibly related to the agent/intervention should be recorded and reported as per sections 7.2, 7.3, 7.4.

An abnormal laboratory value will be considered an AE if the laboratory abnormality is characterized by any of the following:

- Results in discontinuation from the study
- Is associated with clinical signs or symptoms
- Requires treatment or any other therapeutic intervention
- Is associated with death or another serious adverse event, including hospitalization.
- Is judged by the Investigator to be of significant clinical impact
- If any abnormal laboratory result is considered clinically significant, the investigator will provide details about the action taken with respect to the test drug and about the patient's outcome.

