7.1.5 Serious Adverse Event

An adverse event or suspected adverse reaction is considered serious if in the view of the investigator or the sponsor, it results in any of the following:

- Death,
- A life-threatening adverse drug experience
- Inpatient hospitalization or prolongation of existing hospitalization
- Persistent or significant incapacity or substantial disruption of the ability to conduct normal life functions
- A congenital anomaly/birth defect.
- Important medical events that may not result in death, be life-threatening, or require hospitalization may be considered a serious adverse drug experience when, based upon appropriate medical judgment, they may jeopardize the patient or subject and may require medical or surgical intervention to prevent one of the outcomes listed in this definition.

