7.2.2 NCI-IRB Requirements for PI Reporting at Continuing Review

The protocol PI will report to the NCI-IRB:

1. A summary of all protocol deviations in a tabular format to include the date the deviation occurred, a brief description of the deviation and any corrective action.
2. A summary of any instances of non-compliance
3. A tabular summary of the following adverse events:
 - All Grade 2 **unexpected** events that are possibly, probably or definitely related to the research;
 - All Grade 3 and 4 events that are possibly, probably or definitely related to the research;
 - All Grade 5 events regardless of attribution;
 - All Serious Events regardless of attribution.

NOTE: Grade 1 events are not required to be reported.

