7.3 IND SPONSOR REPORTING CRITERIA

An investigator must immediately report to the sponsor, using the mandatory MedWatch form 3500a, any serious adverse event, whether or not considered drug related, including those listed in the protocol or investigator brochure and must include an assessment of whether there is a reasonable possibility that the drug caused the event.

- All Grade 5 (fatal) events (except death due to progressive disease) must be reported via email within 24 hours. A complete report must be submitted within one business day.
- All other serious adverse events including deaths due to progressive disease must be reported within one business day

Study endpoints that are serious adverse events (e.g. all-cause mortality) must be reported in accordance with the protocol unless there is evidence suggesting a causal relationship between the drug and the event (e.g. death from anaphylaxis). In that case, the investigator must immediately report the death to the sponsor.

Events will be submitted to the Center for Cancer Research (CCR) at: [contact] and to the CCR PI and study coordinator.

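### Section 6.1 item 8 leaves post-operative erectile dysfunction and incontinence off the AE record with no limit by grade, seriousness or attribution, which conflicts with the reporting rules in section 7

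*Combined protocol and SAP*

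**What the plan says.** Item 8 of section 6.1 contains two post-operative rules. The first is bounded by grade and by cause: "Post-operatively, we will not report Grades 1 or 2 AEs that are clearly attributable to surgery". Its application is left to the principal investigator. The second has no bound: "Post-operatively, we will not capture erectile dysfunction or incontinence as AEs". The paragraph that follows item 8 exempts perioperative medications from capture, but brings them back if a serious event occurs during surgery.

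Section 7 deals with the same events as follows.

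- 7.1.1, recording: "All AEs must be recorded on the AE case report form unless otherwise noted above in Section 6.1".
- 7.1.1, late events: an SAE more than 30 days after the last dose that is at least possibly related is to be both recorded and reported.
- 7.1.5, seriousness: "An adverse event or suspected adverse reaction is considered serious if in the view of the investigator or the sponsor, it results in any of" a list of outcomes that includes hospitalization.
- 7.2.2, continuing-review table: "All Grade 3 and 4 events that are possibly, probably or definitely related to the research", and also "All Serious Events regardless of attribution".
- 7.3, reports to the IND sponsor: "any serious adverse event, whether or not considered drug related".

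Only the general recording sentence in 7.1.1 refers back to section 6.1.

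**The concern.** Leaving routine, low-grade effects of prostatectomy off the AE form is sensible. The difficulty is that the last sentence of item 8 goes further than that. The rule before it is bounded by grade and attribution, and the medication rule after it makes an exception for serious events. This sentence does neither, so a site that follows it would also leave out a serious case, or one the investigator thought the vaccine might have contributed to.

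The vaccine is intended to produce a T-cell response in the prostate (section 6.2.1.1), and surgery is wanted 7-14 days after the final booster where feasible (section 3.1). Section 1.2.1 says that "no data currently exist with neoadjuvant vaccine in localized prostate cancer". Urinary and sexual function after the operation is one place where an unexpected interaction between vaccine and surgery could appear, though no section predicts one. If these events are not recorded, the safety tables cannot show whether any occurred, and an absence in the tables would not mean that none was seen.

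**Working it through.** The plan states no rate, count or power for these events, so there is no figure of its own to reproduce. The check is a reading of the sections together, followed by a short illustration of scale.

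**Reading the rules together.** Take an illustrative case, not claimed to be typical: a patient is readmitted for incontinence after surgery, and the investigator judges a vaccine contribution possible.

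1. Section 6.1 item 8: not captured as an AE.
2. Section 7.1.1, general sentence: all AEs go on the form except as section 6.1 provides, so the form stays blank.
3. Section 7.1.5: the event led to hospitalization, so it meets the criterion for serious if it is regarded as an adverse event at all. The AE definition in 7.1.1 is broad and item 8 does not rewrite it, so the event still appears to qualify.
4. Section 7.2.2: the event belongs in the table as serious. It also belongs there as possibly related if it is grade 3 or 4. If the table is compiled from AE forms, which the documents do not specify, the event will be missing.
5. Section 7.3: a report to the sponsor is due, with no exception.
6. Section 7.1.1, late-SAE sentence: if the event arises more than 30 days after the last dose, it must be recorded. Both follow-up visits (3-6 and 12-15 months after surgery, section 3.8) fall beyond that point, because surgery itself follows the last dose.

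Steps 1 and 2 say the event is not recorded. Steps 4 to 6 say it is tabulated, reported and, if late, recorded. Nothing states which prevails.

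**Scale.** Inputs: N = 27, the accrual ceiling (section 8), and an assumed true proportion p of patients with a serious or possibly vaccine-related case. The documents give no value for p, so a range is shown.

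Expected cases = 27 × p. Chance of at least one = 1 − (1 − p)^27.

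| Assumed p | Expected cases | Chance of at least one |
|---|---|---|
| 2% | 0.5 | 42% |
| 5% | 1.4 | 75% |
| 10% | 2.7 | 94% |
| 20% | 5.4 | 99.8% |

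These are cases that could arise, not cases that would be lost. The number left off the forms depends on which rule staff follow.

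**What a zero would mean.** A genuinely observed 0 of 27 has an exact two-sided 95% upper limit of 1 − 0.025^(1/27) = 12.8%. A zero that arises because the events were not captured supports no upper limit.

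**The case against.** A reader might infer that these events can never reach the safety reports, so that every case is lost by rule: not an AE, hence not an SAE, hence not reportable. The documents do not support that. The deference in 7.1.1 concerns only what goes on the AE case report form, and the AE definition in that section is unchanged. Item 2 of section 6.1 sends AE reporting to section 7. Section 7.3 and the late-SAE sentence carry no exception, so an investigator who follows them literally would report a serious case. An Unanticipated Problem (7.1.10) can be any incident or outcome that meets its conditions, whether or not it was captured as an AE, and it goes to the IRB and Clinical Director within 7 days (7.2.1). Section 7.6.1 requires safety concerns to be reported at once. All of this stands, and it limits the point to a conflict between sections with possible under-recording. The Unanticipated Problem route is only a partial safeguard: one of its criteria is unexpected frequency, which is hard to judge for events that are not recorded.

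Other objections also stand. The grade 3-4 line in 7.2.2 covers only events at least possibly related to the research, and patients had already chosen prostatectomy (2.1.1.3), so purely surgical cases may fall outside it. Section 10.4 mentions pox-vector PSA vaccines as neoadjuvant therapy with radiation, so the statement in 1.2.1 should not be read as an absence of all related experience. The exclusion is stated openly, so it cannot be assumed that the oversight bodies would take a zero as observed. There is no comparator, and the study calendar lists no baseline continence or potency instrument.

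It is also fair to call the exclusion a deliberate choice in a small trial with an immunologic endpoint. That justifies leaving out routine surgical effects. It does not explain why serious or possibly vaccine-related cases are treated the same way.

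**Conclusion.** The point holds as a conflict between section 6.1 item 8 and section 7. Depending on which section staff follow, serious or possibly vaccine-related erectile dysfunction or incontinence after surgery may be left off the AE forms and out of the safety tables. The stronger conclusion, that all such events are certain to be lost, does not hold.

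The size cannot be fixed from the documents. The 2% to 20% range is an assumption used only for scale, and the rate that matters, that of serious or possibly vaccine-related cases, is unknown. The rule applies only after surgery; the same events between vaccination and surgery are still recorded. The primary endpoint, its analysis and the sample size are unaffected. This is a modest but inexpensive improvement to safety capture.

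**What to change.** Reconcile section 6.1 with section 7 by limiting the last sentence of item 8. Possible wording:

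*Post-operatively, erectile dysfunction or incontinence that is clearly attributable to surgery and not serious will not be captured as an AE. Any such event that is serious, or at least possibly related to the vaccine, will be recorded and reported per 7.2-7.4.*

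The histories already scheduled at 3-6 and 12-15 months after surgery (section 3.8) can supply the information, so no new visit or instrument is needed. The change affects recording and reporting only.

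The wording would still leave out non-serious, purely surgical cases of any grade. That is looser than the grade 1-2 limit in the first rule of item 8, and the sponsor should confirm that it is intended.

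The cost is one sentence in an amendment and a few more AE forms. Some of the recorded events will be ordinary surgical effects, and a single arm cannot separate those from any effect of the vaccine.
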